## 6 STUDY PROCEDURES

### 6.1 Study Procedures by Visit

During study visits, unless otherwise indicated, it is preferred that all assessments including labs and PEs be completed predialysis for subjects on HD. For subjects on HHD and PD, assessments may be completed at any time during the visit, but preferably approximately at the same time of the day at each study visit. Quality of life assessments should be administered approximately at the same time of the day. For example, in subjects on HD, these assessments should be completed approximately at the same time during dialysis and in subjects on HHD/PD approximately at the same time of the day. Weight assessment in HD subjects should be done after dialysis (dry weight). Blood pressure and HR should be assessed according to the guidelines described in [Appendix 5](#).

#### 6.1.1 Screening Period (Up to 6 Weeks)

Subjects must have a signed written informed consent before any screening tests or assessments are performed. For all screen failures, the reason(s) will be documented. Subjects will undergo at least two screening visits to determine eligibility, at least two days apart. All assessments and their timing are outlined in [Appendix 3](#).

##### 6.1.1.1 Screening 1

- Signed written informed consent
- Inclusion/Exclusion criteria verification
- Demographics and medical history
- Complete physical exam
- Height, weight (HD subjects: use dry weight)
- Blood pressure, HR
- Laboratory tests:
  - Complete blood count (CBC) with WBC differential
  - Serum chemistry
  - Lipid panel (fasting whenever possible)
  - Serum iron, ferritin, TIBC, TSAT
  - CHr
  - Hemoglobin A1c (HbA1c)
  - Vitamin B12 and folate (if no value available within 8 weeks prior to randomization)

- Enzyme-linked immunosorbent assay (ELISA) for HIV
- Hepatitis B surface antigen and anti-HCV Ab
- Serum human chorionic gonadotropin (hCG) test for women of childbearing potential only (For definition, see [Section 3.6.6](#)).
- Adverse event recording
- Concomitant medication recording
- Procedures and nondrug therapy recording

### 6.1.1.2 Screening 2

Hemoglobin values must be obtained at least 2 days apart

- Blood pressure, HR
- Hemoglobin only
- Renal ultrasound - not required if results of a previous renal ultrasound or other renal imaging modality within 12 weeks prior to randomization to rule out renal cell carcinoma are available. If no results are available, a renal ultrasound must be performed during screening.
- Adverse event recording.
- Concomitant medication recording
- Procedures and nondrug therapies recording

### 6.1.1.3 Additional Screening

If a subject's laboratory results do not meet the eligibility criteria at Screening, the laboratory assessment may be repeated within the Screening Period.

For example, additional Hb values may be collected if necessary. The mean of 2 most recent Hb values during the screening period, obtained at least 2 days apart, will be used to calculate the subject's eligibility. Liver function test (LFT) parameters may not be repeated if found exclusionary at screening without prior approval from the Medical Monitor, unless the Investigator has a valid reason to believe that the original laboratory result is due to an error (eg, possible sample mix-up). Such a repeat should be communicated to the Medical Monitor as soon as possible.

Screening procedures that are not done at the scheduled visit must be completed prior to randomization.

If subjects fail screening, they may be re-screened once as deemed appropriate by the investigator. Where possible, an approval should be obtained from the Medical Monitor prior to rescreening.

## 6.1.2 Treatment Period

Eligible subjects will be randomized via IXRS to receive roxadustat or epoetin alfa. The Treatment Period begins on the first day of dosing with study treatment (Day 1/Week 0). A common closeout will occur when a predetermined number of adjudicated CV, cerebrovascular or thromboembolic events have been accrued across the entire Phase 3 program.

### 6.1.2.1 Day 1 (Week 0)

All assessments are to be completed prior to study drug administration

- Inclusion/Exclusion criteria verification
- Complete PE
- Weight (HD use dry weight)
- Blood pressure, HR, temperature, and respiratory rate (RR)
- Laboratory tests:
  - Complete blood count with WBC differential
  - Serum chemistry
  - Lipid panel (fasting, whenever possible)
  - Serum iron, ferritin, TIBC, TSAT
  - CHr
  - HbA1c
  - Reticulocyte count
  - Special laboratory analytes: Hepcidin and high sensitivity-C-reactive protein (hs-CRP)
  - Archival serum/plasma samples (optional donation, separate consent form)
- HemoCue®/CritLine® assessment
- 12-Lead ECG
- HRQoL questionnaires (SF-36, FACT-An, and European Quality of Life in 5 Dimensions, 5 Levels [EQ-5D-5L])
- Adverse event recording
- Concomitant medication recording
- Procedures and nondrug therapy recording
- Dispense study drug

### 6.1.2.2 Weeks 1 to 4 (Weekly, $\pm 2$ days)

- Laboratory tests (must be performed prior to dosing):
  - Weeks 1, 2, 3, 4, CBC with WBC differential.
  - Week 2: LFTs only
  - Week 4: Serum chemistry
  - Week 4: Lipid panel (fasting whenever possible)
  - Week 4: Serum iron, ferritin, TIBC, TSAT.
  - Week 4: CHr
  - Weeks 1, 2: Reticulocyte count
  - Week 4: Special laboratory analytes
  - Week 4: Archival serum/plasma samples (optional donation, separate consent form)
- HemoCue®/CritLine® assessment.
- Dose adjustment review beginning Week 4 and at 4-weekly intervals thereafter (except in the event of excessive hematopoiesis). Refer to [Section 3.5.3](#), and [Appendix 2](#).
- All visit weeks: BP and HR
- Adverse event recording
- Concomitant medication recording
- Procedures and nondrug therapy recording
- Dispense study drug every 2 weeks (Week 2 and Week 4)

### 6.1.2.3 Weeks 6 to 24 (Every 2 weeks, $\pm 4$ days)

- Laboratory tests (must be performed prior to dosing):
  - Weeks 8, 12, 20: CBC with WBC differential
  - Week 6 followed by every visit where no CBC is collected; Hb only.
  - Weeks 8, 12, 20: Serum chemistry
  - Weeks 6, 16: LFTs and CPK
  - Weeks 8, 12, 24: Lipid panel (fasting whenever possible).
  - Weeks 8, 12, 20: Serum iron, ferritin, TIBC, TSAT.
  - Weeks 8, 12, 20: CHr
  - Week 12: HbA1c
  - Weeks 8, 20: Reticulocyte count
  - Weeks 12, 20: Special laboratory analytes

- Weeks 12, 20: Archival serum/plasma samples (optional donation, separate consent form)
- HemoCue®/CritLine® assessment
- Weeks 12, 24: Serum hCG pregnancy test for women of childbearing potential (for definition, see [Section 3.6.6](#))
- 
- Week 24 followed by every 12 weeks: Targeted physical exam (eg, respiratory and cardiovascular system)
- Week 24 followed by every 24 weeks: 12-lead ECG, weight (HD subjects: dry weight)
- Dose adjustment review every 4 weeks (except in the event of excessive hematopoiesis or dose frequency conversion). Refer to [Section 3.5.2](#), and [Appendix 2](#).
- All visit weeks: BP and HR
- Week 12 HRQoL questionnaires (SF-36, FACT-An, and EQ-5D-5L)
- Adverse event recording
- Concomitant medication recording
- Procedures and nondrug therapy recording
- Dispense study drug

#### 6.1.2.4 Weeks 28 to End of Therapy (Every 4 weeks, ±4 days)

- Laboratory tests (must be performed prior to dosing):
  - Week 28 followed by every 8 weeks: CBC with WBC differential
  - Week 32 followed by every visit where no CBC is collected; Hb only
  - Week 28 followed by every 8 weeks: Serum chemistry
  - Weeks 32, 40, 48, 60 followed by every 24 weeks: Lipid panel (fasting whenever possible)
  - Week 28 followed by every 8 weeks: Serum iron, ferritin, TIBC, TSAT
  - Week 28 followed by every 8 weeks: CHr
  - Weeks 28, 44, 60, followed by every 16 weeks: HbA1c
  - Week 44 followed by every 24 weeks: Reticulocyte count
  - Week 44, followed by every 24 weeks: Special laboratory analytes

- Week 44 followed by every 24 weeks: Archival serum/plasma samples (optional donation, separate consent form)
- All visit weeks: HemoCue®/CritLine® assessment.
- Week 36 followed by every 12 weeks: Targeted physical exam (eg, respiratory and cardiovascular system)
- Week 36, followed by every 12 weeks: Serum hCG test for women of childbearing potential (for definition, see [Section 3.6.6](#))
- All visit weeks: Dose adjustment review (except in the event of excessive hematopoiesis or dose frequency conversion). Refer to [Section 3.5.2](#), and [Appendix 2](#).
- All visit weeks: BP and HR
- Weeks 36 and 52: HRQoL questionnaires (SF-36, FACT-An, and EQ-5D-5L)
- Adverse event recording
- Concomitant medication recording
- Procedures and nondrug therapy recording
- Dispense study drug

\* If the indicated assessments fall on a study treatment visit that is within two weeks of the planned EOT visit, then these specified assessments can be postponed until the EOT visit.

#### 6.1.2.5 End of Treatment ( $\pm$ 7 days)

- Laboratory tests:
  - Complete blood count with WBC differential
  - Serum chemistry
  - Lipid panel (fasting whenever possible)
  - Serum iron, ferritin, TIBC, TSAT
  - CHr
  - HbA1c
  - Reticulocyte count
  - Special laboratory analytes
  - Archival serum/plasma samples (optional donation, separate consent form)
- Complete physical exam.

- Serum hCG test for women of childbearing potential (for definition, see [Section 3.6.6](#))
- Blood pressure, HR, temperature, respiration rate
- HRQoL questionnaires (SF-36, FACT-An, and EQ-5D-5L)
- 12-lead electrocardiogram
- Adverse event recording
- Concomitant medication recording
- Procedures and nondrug therapy recording

Erythropoiesis-stimulating agents may be started  $\geq$  3 days after the last dose of roxadustat.

#### **6.1.2.6 Early Termination (ET)**

If a subject discontinues study medication permanently during the Treatment Period, perform the EOT assessments at the time of withdrawal from dosing or as soon as possible ([Section 6.1.2.5](#)). Erythropoiesis-stimulating agents may be started  $\geq$  3 days after the last dose of roxadustat.

Unless consent is withdrawn, these subjects will be followed up for CV events of interest, vital status, and hospitalization until study closure.

These subjects will be followed up every 3 to 6 months (depending on the availability of the subjects) until study closure. These visits may occur either in person or via telephone.

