### 7.3 Additional Evaluation of Efficacy

- **Hemoglobin Correction and Maintenance:**
  - Hemoglobin maintenance: Mean change in Hb averaged over 8 weeks of treatment at Weeks 28 to 52, without rescue therapy within 6 weeks prior to and during this 8-week evaluation period.
  - Hemoglobin long-term Maintenance: Mean change in Hb averaged over 8 weeks of treatment at Weeks 44 to 52 without rescue therapy within 6 weeks prior to and during this 8-week evaluation period
  - Mean change in Hb averaged over the 96 to 104 weeks of treatment, without rescue therapy within 6 weeks prior to and during this 8-week evaluation period
  - Change in Hb at each of the selected time points
  - Change in Hb averaged over 8 weeks of treatment at Weeks 28 to 36, without rescue therapy within 6 weeks prior to and during this 8-week evaluation period, in subjects who have reached a Hb  $\geq 11$  g/dL prior to Week 28
  - Proportion of subjects with Hb within 10 to 12 g/dL in United States and 10 to 13 g/dL in Ex-US averaged over Weeks 28 to 36, without rescue therapy within 6 weeks prior to and during this 8-week evaluation period
- **Hospitalizations:**
  - Occurrence (number) of hospitalization(s)
  - Proportion of subjects hospitalized
  - Number of days of hospitalizations per patient-exposure year (PEY)
- Missed dialysis sessions

- **Rescue Therapy Use:**
  - Proportion of subjects who receive RBC transfusions
  - Number of RBC packs per patient-month exposure to study medication
  - The proportion of subjects requiring ESA rescue therapy will be summarized
- **Changes in Cholesterol Levels:**
  - Change at each of the selected treatment time points in:
    - Total cholesterol
    - LOL/HDL ratio
    - Non-HDL cholesterol.
  - Proportion of subjects achieving LDL target of < 100 mg/dL averaged over Weeks 12 to 24 of treatment.

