- k All assessments should be done prior to first study drug administration.
- l Dispense every other week
- m Subjects who prematurely discontinue study treatment will complete the ET and EOS visits, and – unless consent is withdrawn – will continue to be followed for CV events of interest, vital status and hospitalizations until study closure. These subjects will be asked to return for study visits every 3 to 6 months, or be available via telephone.

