11 EFFICACY ANALYSES

Efficacy analysis will be conducted on the ITT and FAS for US (FDA) submission and analysis for non-inferiority on the PPS population and analysis for superiority on FAS population for EU regulatory submission.

The **Efficacy Emergent Period** is defined as the evaluation period from the Analysis date of first dose intake up to 7 days after the Last Dose of study drug or EOT Visit, whichever occurs first. This period will be used as reference period for the time to event analyses related to efficacy endpoints, unless specified otherwise.

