11.3.2 Hospitalizations (including skilled nursing facility)

Hospitalizations are collected in the Hospitalization Records Form of the eCRF. For each subject, an entry will be recorded for each hospitalization. The days of hospitalization will be calculated as the sum of all hospitalizations durations in days (Date of discharge – Date of Admission + 1). In case of missing dates, the hospitalization duration will be assumed to be 5 days.

Only hospitalizations with admission dates that occur during the treatment period and up to 7 days after the last study medication date will be taken into account.

The following hospitalization-related data will be analyzed and compared between the 2 treatment groups:

- Time to first hospitalization up to Week 52- Proportion of subjects hospitalized. Time to first hospitalization or skilled nursing facility up to Week 52.
- Number of days of hospitalizations
- Number of days of medical-facility
- Number of days of hospitalizations per patient-exposure year (PEY).
- Number of days in hospital or skilled nursing facility per patient-year exposure (PEY)
- Number of days of medical-facility per subject-exposure year (PEY).

- Number of days on treatment out of hospital and skilled nursing facility up to Week 52, 7 days after Last Dose. The days will be compared between the 2 treatment groups using ANCOVA model with baseline Hb and the baseline stratification factors.

Note: Elective procedures may be excluded from analyses by using only hospitalization due to AE.

The time to hospitalization event will be compared between the two treatment groups using cox model including baseline stratification factors. The proportion of subjects hospitalized will be compared between the 2 treatment groups using logistic regression model and stratified by the baseline stratification factors. The mean number of days of hospitalization will be analyzed and compared between the 2 treatment groups using the Mantel-Haenszel mean score test adjusting for stratification factors.

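### SAP 11.3.2 counts admissions only up to 7 days after last dose, so hospitalizations that the protocol collects after early termination go unused and the between-arm comparison is exposed to unequal stopping

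*Protocol*

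**What the plan says.** **Collection.** Protocol 6.1.2.6 covers subjects who permanently stop study drug: "Unless consent is withdrawn, these subjects will be followed up for CV events of interest, vital status, and hospitalization until study closure." Footnote m of protocol Appendix 3 says that they "will continue to be followed for CV events of interest, vital status and hospitalizations until study closure", and footnote m of SAP Appendix 1 repeats the rule. Contact is every 3 to 6 months, in person or by telephone.

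**Endpoint.** Protocol 7.3 lists the number of hospitalizations and "Proportion of subjects hospitalized" with no last-dose limit; only hospital days are expressed per exposure year. SAP 4.4 sets time to first hospitalization up to Week 52, again with no last-dose limit. The one SAP 4.4 hospitalization item tied to last dose is the count of days on treatment spent out of hospital.

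**Analysis.** SAP 11.3.2 takes into account "Only hospitalizations with admission dates that occur during the treatment period and up to 7 days after the last study medication date". It then states: "The time to hospitalization event will be compared between the two treatment groups using cox model including baseline stratification factors." For the other measure: "The proportion of subjects hospitalized will be compared between the 2 treatment groups using logistic regression model", stratified by the baseline factors, with no adjustment for observation time. SAP section 11 sets a similar default period for efficacy time-to-event analyses, running "up to 7 days after the Last Dose of study drug or EOT Visit, whichever occurs first".

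**Status.** Hospitalization is an additional efficacy evaluation in the FAS. It is not in the fixed sequence of SAP Table 5, and SAP 5.3 makes no multiplicity adjustment for it.

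**The concern.** An endpoint described as running to Week 52 is analysed as an on-treatment endpoint without being called one. A subject who stops in month 2 and is admitted in month 4 counts as never hospitalized in the logistic model and is censored in the Cox model, although the protocol asks the site to record that admission.

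This matters if the arms differ in how often, or in whom, treatment stops. The trial is open-label. The reasons for discontinuation in protocol 6.1.3.2 include adverse events, investigator decision and kidney transplant, together with a lack-of-efficacy reason tied to ESA rescue that applies to roxadustat only. Different stopping patterns are therefore plausible. Under the 7-day rule the comparison would then partly reflect who stopped and when, although data that would largely avoid this are already being collected.

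**Working it through.** The plan gives no hospitalization rate, stopping rate, event count or power, so there is no stated figure to reproduce. Every rate below is an assumption chosen to show how the rule behaves.

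**Step 1: proportion hospitalized, stopping unrelated to illness (exact).** Let the admission hazard be 1.0 per year in both arms, before and after stopping. Let the stopping hazard be s per year and the window be w = 7/365.25 = 0.01916 years. The probability that a first admission is counted by one year is

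P(s) = 1 − e^(−w) + e^(−w) × [1 − e^(−(1+s)(1−w))] / (1+s)

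- s = 0.25: 0.01898 + 0.98102 × (1 − 0.2935)/1.25 = 0.01898 + 0.98102 × 0.5652 = 57.3%
- s = 0.35: 0.01898 + 0.98102 × (1 − 0.2660)/1.35 = 0.01898 + 0.98102 × 0.5437 = 55.2%
- True one-year proportion in both arms: 1 − e^(−1) = 63.2%

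The arms are identical in risk, yet the counted proportions differ by 2.1 points. The arm that stops more looks better only because it is observed for less time.

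**Step 2: both measures, simulated under a true hazard ratio of 1 (300,000 subjects per arm).** Assumed: 30% sicker subjects with 2.0 admissions per year and the rest with 0.5, the same in both arms. Arm C stops at 0.25 per year unless stated; arm A varies.

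| Stopping pattern | Cox HR, A vs C, 7-day rule | Proportion, A vs C, 7-day rule |
|---|---|---|
| Same in both arms (sicker 1.0/yr, others 0.25/yr) | 1.00 | 44.2% vs 44.2% |
| A: everyone stops at 0.75/yr | 1.00 | 41.0% vs 48.8% |
| A: sicker stop at 0.75/yr | 0.96 | 45.5% vs 48.8% |
| A: sicker stop at 1.5/yr | 0.91 | 41.8% vs 48.5% |
| A: healthier stop at 0.75/yr | 1.06 | 44.3% vs 48.6% |
| Stop triggered by a counted admission (30% of admissions in A, 10% in C) | 1.00 | 48.6% vs 48.5% |
| Milder gradient (1.2 vs 0.8/yr), A: sicker stop at 0.75/yr | 0.98 | 50.8% vs 54.0% |

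When all admissions to Week 52 are counted, every row returns a hazard ratio of 1.00 and proportions that agree to within 0.2 points: about 53.5% in both arms, or 59.5% in the last row.

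**Reading the table.** The Cox result moves only when stopping is related to admission risk and differs by arm, and it can move either way. The proportion falls in the arm that stops more, whoever stops, unless the stop follows an admission already counted. In the row where healthier subjects stop, the two SAP analyses point in opposite directions (hazard ratio 1.06 against arm A, proportion 4.3 points in its favour) although nothing differs between the arms except stopping.

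**The case against.** The best defence is that the window is a deliberate, pre-specified on-treatment definition. It matches the default period in SAP section 11 and the exposure-year denominator in SAP 9.1, which ends at last dose. After stopping, roxadustat subjects may start an ESA from 3 days after the last dose, so full follow-up mixes in time on the control drug class. Collecting more than is analysed is not in itself an error. Heart failure and unstable angina admissions are also adjudicated for pooled plans that are not available here. All of this stands, and it is why the on-treatment version should be kept. It does not explain why that version is the only one, or why an endpoint set to Week 52 carries no on-treatment label.

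A reader might infer more: that sicker roxadustat subjects stop more often, so the rule flatters roxadustat. The documents do not support this. The roxadustat-only reason concerns more than one ESA rescue course for inadequate Hb response, and protocol 3.6.3.2 requires causes such as bleeding and acute inflammation to have been ruled out before rescue. Kidney transplant, another listed reason, need not mark a sicker subject.

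Nor does modelling establish the inference. Suppose illness-driven stopping at 0.20 per year on roxadustat and 0.10 on epoetin, unrelated stopping at 0.15 in both arms, and an admission hazard of 3 to 5 after an illness-driven stop. The 7-day rule then gives 55.6–56.0% against 57.5–57.8%, with a rate ratio of 1.00–1.01. That gap is nearly the one in Step 1 (55.2% against 57.3%), where illness plays no part. It reflects observation time, not a biased hazard ratio.

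**Conclusion.** The mismatch between collection and analysis is plain in the text. The logistic proportion is the more exposed measure, because unequal stopping alone is enough to distort it. The Cox comparison is affected only if stopping also tracks admission risk differently by arm. Under assumed rates and no true difference, the distortion ranges from nothing to 7.8 points in the proportion (41.0% against 48.8%), and the hazard ratio lies between 0.91 and 1.06.

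These figures illustrate the mechanism; they are not predictions. Neither document gives stopping or admission rates, so which arm would benefit, and by how much, cannot be said. With the same stopping pattern in both arms there is no bias. The endpoint lies outside the fixed sequence, so the primary and key secondary conclusions are untouched. This is a worthwhile and inexpensive improvement to an additional endpoint.

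**What to change.** In SAP 11.3.2:

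- Add a between-arm analysis of time to first hospitalization and of the proportion hospitalized that uses all admissions from first dose to Week 52, regardless of treatment stop. Censor at the earliest of Week 52, study closure, withdrawal of consent and last contact.
- In that analysis, estimate the proportion by a time-to-event method at Week 52 instead of a logistic model that ignores observation time.
- Report first admission or death alongside, since death prevents later admission.
- Label the existing last dose plus 7 days version as an on-treatment analysis, and present both.

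The cost is SAP text and additional tables on data that the protocol already requires. There are three downsides. Contact every 3 to 6 months makes some admission dates imprecise. Off-drug time, including ESA use after roxadustat, dilutes an on-drug effect. SAP 11.3.2 also allows elective procedures to be excluded by keeping only AE-related admissions, but under protocol 9.3.1 required AE reporting ends 28 days after the ET/EOT visit. That filter cannot be applied reliably afterwards, so the added analysis should be all-cause.
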